5.5 Study Evaluations

We will use standard clinical urodynamics methods for data collection. We will use an FDA-approved modified external controller to communicate with the already-implanted components of the system, so no new surgeries or other procedures are required. The device has been modified to achieve frequencies up to 600 Hz and this modification was approved by the FDA in an IDE. We will document their normal daily usage device settings for reference, including stimulation amplitude, pulse width, frequency, and on/off cycle duration.

Clinical Urodynamics and Anorectal Manometry Procedure: A standard catheter will be inserted into the bladder via the urethra and the bladder will be emptied. This catheter will be removed and then a second catheter, which can measure bladder and urethral pressures, will be inserted. This catheter will also have a lumen for filling the bladder with sterile saline. A balloon catheter inserted in the rectum will be used to reflect abdominal pressure and distinguish bladder pressures due to detrusor contraction versus bladder pressures due to abdominal activity. This balloon catheter will measure rectal pressure. It will also have pressure transducers at the anal sphincter to measure anal sphincter pressure. Surface electromyogram (EMG) electrodes will be applied to the anal sphincter to monitor pelvic floor muscle contractions. Infused volumes will be controlled via an infusion pump. EMG and pressure signals will be monitored on a clinical urodynamic system. The participant's bladder will be infused with sterile saline while measuring bladder, urethral sphincter, and rectal pressures.

Sacral Anterior Root Stimulation: We will set the stimulation parameters for the implanted stimulator, including stimulation amplitude and frequency, using a modified Finetech-Brindley external controller unit. The frequency will be set either to 600 Hz or to the low frequency that the participant typically uses for emptying their bladder, which is usually 20 Hz. We will use the participant's own power transmission coil. The receiver coil and electrodes will already have been implanted. The pulse width will not be changed from the participant's normal setting.

Aim 1: Determine if 600 Hz sacral root stimulation limits contraction of the urethral sphincter.

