During visit 2, in a single session, we will first administer SARS using the stimulation parameters (i.e., frequency, pulse width, and amplitude) that the study participant typically uses to empty their bladder and has been for years. The purpose is to characterize the usual level of urethral sphincter and bladder pressure during their bladder emptying routines and collect these baseline data.

We will also have a frame of reference for stimulation amplitude for testing 600 Hz stimulation.

We will then decrease the stimulation amplitude and identify the threshold amplitude to achieve urethral sphincter contraction at low frequency, which will be compared to the threshold amplitude to evoke bladder contraction. The motor efferents innervating the urethral sphincter are significantly larger in diameter than the motor efferents innervating the bladder, so the thresholds for activating the bladder are higher than for activating the urethral sphincter. These thresholds amplitudes at low frequency will give us additional context for evaluating the recruitment of urethral sphincter and bladder pressures in response to sacral stimulation.

We will then test stimulation at 600 Hz. 600 Hz stimulation will first evoke a brief (~1-2 second) onset respond and then the urethral pressure is expected to return to baseline. The stimulation amplitude will be set to 0 mA and gradually increased to determine the threshold amplitude for evoking an initial onset response of the urethral sphincter. We will continue to increase the stimulation amplitude until we have achieved maximal urethral sphincter pressure onset response. Stimulation will be maintained for up to 10 seconds with at least 30 seconds rest between stimuli. Once this recruitment curve is established, we will repeat stimulation at threshold, 50% maximal recruitment, and 90% maximal recruitment for up to 30 seconds to measure reduction of urethral sphincter pressures.

Aim 2: Determine if 600 Hz sacral root stimulation limits contraction of the anal sphincter.

This aim has the same design as Aim 1 but will focus on bowel function. Data for this aim will be measured during the same session as Aim 1. We will administer SARS using the stimulation parameters and pattern that the participant typically uses to empty their bowel and has been for years. These data will give us context for evaluating effects on bowel function.

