5.6 Data Analysis

Outcomes from urodynamics data will be used to determine the effect of electrical stimulation on limiting urethral and anal sphincter pressures. Distributions of pressures without and with 600 Hz and 20 Hz stimulation will be compared with an ANOVA and a significance level of 0.05. We expect to observe a lower level of urethral and anal sphincter pressure in response to sacral stimulation at frequencies of 600 Hz compared to the low stimulation frequency that participants typically use.

Potential Limitations and Alternative Solutions

If 600Hz sacral stimulation in humans fails to limit urethral and anal sphincter activity compared to what is evoked at low frequency, then we will need to consider alternative stimulation strategies in future studies. We acknowledge that another potential approach using kilohertz frequency stimulation could be considered. Our group and others have tested kilohertz frequency sinusoidal waveforms extensively preclinically to block nerve conduction. This could be another alternative to the rhizotomy, but it would require development and regulatory approval of a new implantable stimulation system that can safely deliver stimulation in the kilohertz frequency range for human testing [14]– [18].

We do not expect to experience significant technical challenges because (1) we are using a SARS system that study participants have been successfully using for years and (2) we are using research methods that we have successfully used for years to collect these data [19], [20]. We may find that the external controller does not deliver sufficient charge to achieve sphincter reduction at elevated stimulation frequencies. This is unlikely because the amplitude required to avoid contraction at 600Hz frequencies is not significantly higher than the amplitude to achieve activation at lower amplitudes.

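### Does section 5.6 need to name the low-frequency run that supplies anal sphincter pressure for Aim 2?

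*Combined protocol and SAP*

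**What the plan says.** Section 5.1 makes anal sphincter pressure the primary outcome of Aim 2. Section 5.5 gives a general rule for the controller: "The frequency will be set either to 600 Hz or to the low frequency that the participant typically uses for emptying their bladder", with 20 Hz given as the usual value of that low frequency.

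Under Aim 1, section 5.5 begins the session with a run at the participant's usual bladder settings, to obtain baseline urethral sphincter and bladder pressures. Under Aim 2 it says "This aim has the same design as Aim 1 but will focus on bowel function" and adds a second usual-setting run: "We will administer SARS using the stimulation parameters and pattern that the participant typically uses to empty their bowel and has been for years". It describes the data from that second run as background for judging effects on the bowel. It does not call them a baseline.

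On measurement, section 5.5 says of the rectal balloon catheter: "It will also have pressure transducers at the anal sphincter to measure anal sphincter pressure". It also says "EMG and pressure signals will be monitored on a clinical urodynamic system".

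Section 5.6 states the analysis for both sphincters together: "Distributions of pressures without and with 600 Hz and 20 Hz stimulation will be compared with an ANOVA and a significance level of 0.05". The expected result is lower pressure at 600 Hz "compared to the low stimulation frequency that participants typically use". The limitations paragraph considers what follows if 600 Hz "fails to limit urethral and anal sphincter activity compared to what is evoked at low frequency".

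**The concern.** The analysis has one low-frequency level, but the session has two runs that could supply it for the anal sphincter. The bladder-setting run fits the controller rule in section 5.5, the 20 Hz label in section 5.6 and the Abstract, which describes baseline data at bladder-management settings only. The bowel-setting run fits the statement that Aim 2 shares the design of Aim 1, because it comes directly before the 600 Hz tests, where the Aim 1 baseline run stands.

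The controller rule also mentions no bowel setting, so at first sight sections 5.5 and 5.6 seem to disagree about what is done.

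At stake is the reference value for a primary outcome. If each participant has two usual-setting anal pressures and the plan names neither, the choice could be made after the data are seen.

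**Working it through.** No figure in the plan depends on this point: the sample size of 8 comes with no power, effect size or standard deviation. The check sets the passages side by side and counts.

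**1. Do the sections disagree about which runs take place?** Only the Aim 1 and Aim 2 parts of section 5.5 set out the session, and they describe both usual-setting runs. The controller paragraph states how the frequency is set. Section 5.6 lists conditions to be analysed; a run missing from that list is not thereby denied. The controller rule conflicts with the bowel run only if the bowel frequency differs from the bladder frequency. The documents do not give the bowel frequency, so a contradiction is possible but not shown.

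**2. Is 20 Hz a different condition from the participant's own low frequency?** Section 5.5 gives 20 Hz as the usual value of the bladder-emptying frequency. Section 5.6 writes 20 Hz in one sentence and the habitual frequency in the next. The second reads most simply as the definition and the first as its shorthand.

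**3. Could either run supply an anal pressure?** The transducers sit on the rectal catheter, and signal monitoring is not restricted by run. One sentence, on pressures measured while the bladder is filled, lists bladder, urethral sphincter and rectal pressures and omits anal pressure. It concerns filling and does not exclude recording anal pressure during stimulation. Availability under both readings is therefore a reasonable inference, though not an explicit statement.

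**4. How much of the analysis turns on the choice?** The conditions are none, 600 Hz and low frequency.

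- Pairwise contrasts per sphincter: 3 × 2 / 2 = 3.
- Over two sphincters: 3 × 2 = 6.
- Contrasts that are both anal and involve low frequency: 2 (none against low, 600 Hz against low).
- Unaffected: 6 − 2 = 4, namely all three urethral contrasts and anal 600 Hz against none.

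The overall ANOVA for the anal sphincter would also use the chosen run. The urethral ANOVA would not change.

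**5. What decision rests on it?** The limitations paragraph of section 5.6 says only that other stimulation strategies would have to be considered in later work. The follow-on project described at the end of section 5.1 depends on a reduction in urethral sphincter pressure; anal pressure is not mentioned. The Abstract presents Aim 2 as an opportunity taken within a pilot.

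**6. Could some participants lack a bowel run?** Eligibility in section 5.4 requires bladder use of the device only, and the Abstract asks everyone to take part in both aims. The Aim 2 wording presupposes a usual bowel setting. The documents give no count of participants without one, so no loss of data can be claimed. The question does not arise if the bladder-setting run is the reference.

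**The case for a change.** The strongest contrary case is that careful readers can reach different answers from the same text, which is what a plan should prevent for a primary outcome. Equal frequencies would not settle it either: the bowel run is defined by its parameters and pattern, so amplitude, pulse width or on/off cycle could differ and the two anal values could differ with them. The stated purpose of the bladder-setting run names urethral sphincter and bladder pressure but not anal pressure, while the bowel data are described only as background. Neither run is assigned the role, and naming one would take a few sentences at no cost in runs, visits or participants.

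The ambiguity and the possibility of choosing after the fact both stand. An error does not. Either run can be defended as a within-person reference, neither can be shown from the documents to be wrong, and the remedy would only record a choice between two acceptable options. The objection offers no better method and no rule or number in the plan that would mislead.

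**Conclusion.** This is a gap that analysts can fill sensibly, and no change to the plan follows. The low-frequency run for anal sphincter pressure is unnamed, and the low-frequency condition is worded in more than one way across sections 5.5 and 5.6. The effect is confined to two of six pairwise contrasts and the overall anal test, in a case series of 8 people acting as their own controls. With so few participants, the report can identify the run used and show anal pressures from both, so a reader can see whether the choice matters.

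This conclusion assumes that anal pressure is recorded during both usual-setting runs, which the equipment description supports without saying so outright. It assumes nothing about the bowel frequency or the number of participants with a bowel setting, and takes no position on which setting should be used.

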5.6 Data Analysis

Outcomes from urodynamics data will be used to determine the effect of electrical stimulation on limiting urethral and anal sphincter pressures. Distributions of pressures without and with 600 Hz and 20 Hz stimulation will be compared with an ANOVA and a significance level of 0.05. We expect to observe a lower level of urethral and anal sphincter pressure in response to sacral stimulation at frequencies of 600 Hz compared to the low stimulation frequency that participants typically use.

Potential Limitations and Alternative Solutions

If 600Hz sacral stimulation in humans fails to limit urethral and anal sphincter activity compared to what is evoked at low frequency, then we will need to consider alternative stimulation strategies in future studies. We acknowledge that another potential approach using kilohertz frequency stimulation could be considered. Our group and others have tested kilohertz frequency sinusoidal waveforms extensively preclinically to block nerve conduction. This could be another alternative to the rhizotomy, but it would require development and regulatory approval of a new implantable stimulation system that can safely deliver stimulation in the kilohertz frequency range for human testing [14]– [18].

We do not expect to experience significant technical challenges because (1) we are using a SARS system that study participants have been successfully using for years and (2) we are using research methods that we have successfully used for years to collect these data [19], [20]. We may find that the external controller does not deliver sufficient charge to achieve sphincter reduction at elevated stimulation frequencies. This is unlikely because the amplitude required to avoid contraction at 600Hz frequencies is not significantly higher than the amplitude to achieve activation at lower amplitudes.

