3.0 Objectives

The objective of this study is to test the potential effectiveness of 600 Hz sacral root stimulation to limit urethral sphincter activity in individuals with neurogenic bladder dysfunction (Aim 1). We hypothesize that sacral root stimulation at 600 Hz will result in lower urethral sphincter pressures compared to pressures in response to stimulation at the lower frequencies that are typically used for SARS. We will also test if this stimulation similarly limits anal sphincter activity (Aim 2). Individuals will already have received an implanted SARS device and will have also received a rhizotomy.

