5.0 Study Procedures

5.1 Study Design

In this 2-year case series study, we will enroll 8 participants, male or female, who have SCI and who already use implanted sacral root anterior stimulation to manage their bladder. Participants will act as their own controls.

If a participant is a Veteran, then they will complete study visits at the Cleveland VA Medical Center. If they are not a Veteran, then they will complete study visits at MetroHealth Medical Center for which we already have an approved IRB protocol.

During an initial study visit, expected to take about one hour, we will obtain informed consent. Then a sample of urine will be collected and tested to determine if they have a urinary tract infection.

In the days following this initial visit, subjects will be prescribed an antibiotic, which they will pick up from Pharmacy, to take in the days before and after participation in this study to prevent a urinary tract infection. We will contact subjects in the days leading up to the second visit to remind them of the antibiotic.

A second study visit will then occur 2-30 days later and last about 4 hours. Stimulus waveforms for urethral sphincter inhibition will be tested in the clinical laboratory in a single session. We will not need to conduct new surgeries or implant procedures. The primary outcome measure is urethral sphincter pressure, and additional outcome measures include bladder pressure, rectal pressure, and bladder volume as measured in clinically standard urodynamics examination. The primary outcome measure for Aim 2 is anal sphincter pressure.

Clinical Impact

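### The ANOVA in Section 5.6 does not test the plan's own hypothesis, that sphincter pressure is lower at 600 Hz than at the participant's usual low frequency

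*Combined protocol and SAP*

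**What the plan says.** Section 3.0 sets the hypothesis, with the usual SARS settings as comparator: "We hypothesize that sacral root stimulation at 600 Hz will result in lower urethral sphincter pressures compared to pressures in response to stimulation at" (the sentence then names that comparator). Section 5.6 repeats it for both sphincters as an expectation, "We expect to observe a lower level of urethral and anal sphincter pressure in response to sacral stimulation at frequencies of 600 Hz", relative to the participant's usual low frequency. Its limitations paragraph uses the same comparison to describe failure: 600 Hz "fails to limit urethral and anal sphincter activity compared to what is evoked at low frequency".

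The only inferential statement is in Section 5.6: "Distributions of pressures without and with 600 Hz and 20 Hz stimulation will be compared with an ANOVA and a significance level of 0.05". No contrast, post-hoc test, sidedness or decision rule accompanies it there or elsewhere in the text available. (Sections 1.0 and 4.0, on personnel and resources, are not in that text.)

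The design is within-person: "Participants will act as their own controls" (Section 5.1). Section 5.5 has two stimulation settings: "The frequency will be set either to 600 Hz or to the low frequency that the participant typically uses for emptying their bladder". For Aim 1 it also plans to "identify the threshold amplitude to achieve urethral sphincter contraction at low frequency", which takes for granted that low frequency contracts the sphincter.

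**The concern.** With two stimulation settings, the word 'without' in the analysis sentence most naturally adds rest as a third condition. An overall F test on three conditions asks whether any of the means differ. The plan already expects low-frequency pressure to exceed resting pressure. A significant F is therefore likely, when that rise is large relative to the noise, whether or not 600 Hz does anything useful. If 600 Hz has no limiting effect, both stimulated conditions sit above rest, and stimulation versus rest drives the result.

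What is at stake is the conclusion drawn. Section 5.1 (Clinical Impact) makes the next project, implantation without rhizotomy, conditional on this study showing a fall in urethral sphincter pressure at 600 Hz. The plan does not say which test supplies that evidence.

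**Working it through.** **Inputs from the documents.** 8 participants, each their own control (Section 5.1); significance level 0.05 (Section 5.6); two stimulation settings plus rest (Sections 5.5 and 5.6). The plan gives no power figure to reproduce.

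**Assumptions.** The documents give no SD or effect size. I take one value per participant per condition, equal and independent within-person errors, and low-frequency pressure D within-person SDs above rest, with D = 0.5, 1, 1.5, 2.

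**Step 1: the two outcomes that matter.** Order the means as rest, low frequency, 600 Hz.
- Success, 600 Hz fully back to rest: (0, D, 0). Grand mean D/3. Sum of squared deviations (1/9 + 4/9 + 1/9)D² = (2/3)D².
- Failure, 600 Hz no different from low frequency: (0, D, D). Grand mean 2D/3. Sum of squared deviations (4/9 + 1/9 + 1/9)D² = (2/3)D².

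The sums are identical. Under equal variances and one value per condition, this holds for any D.

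**Step 2: chance that the ANOVA gives p<0.05.** Repeated-measures F on 2 and 14 df, critical value 3.74, noncentrality 8 × (2/3) × D².

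| D | Noncentrality | P(p<0.05), success | P(p<0.05), failure |
|---|---|---|---|
| 0.5 | 1.33 | 14% | 14% |
| 1 | 5.33 | 44% | 44% |
| 1.5 | 12.0 | 80% | 80% |
| 2 | 21.33 | 97% | 97% |

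Simulation with 200,000 replicates agrees.

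**Step 3: what the team might do next.** The plan states no follow-up rule, so I simulated two, and compared them with the paired contrast used alone. For that contrast the difference has SD √2, so the noncentrality is √8 × D/√2 = 2D, that is 1, 2, 3, 4, on 7 df. False success means declaring a reduction when 600 Hz equals low frequency. Detection means declaring one when 600 Hz returns pressure to rest.

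| Rule | False success, D = 0.5, 1, 1.5, 2 | Detection, same D |
|---|---|---|
| Significant F plus a lower 600 Hz mean | 7, 22, 40, 48% | not the issue here |
| Significant F, then a significant paired test | 1.5, 2.1, 2.4, 2.5% | 8, 33, 69, 92% |
| Paired contrast alone, two-sided 0.05, negative difference | 2.5% throughout | 14, 41, 73, 93% |

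False success thus runs from about 2% to 48% depending on a rule that is not written down. The paired contrast alone holds it at 2.5% and detects a full return to rest more often than F followed by a paired test.

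**The case against.** **The comparison is already stated.** The sentence after the ANOVA gives the comparison and its direction, so the question of interest is not in doubt. That stands, and it would be wrong to say that the plan never names its comparison. But the sentence is an expectation, and no text turns it into a test.

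**It may be a two-level ANOVA.** If only 600 Hz and low frequency were meant, a repeated-measures ANOVA equals the two-sided paired test and the problem goes away. The phrase 'without and with' does not read that way, but one sentence would settle it.

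**It may be a stimulation-by-frequency layout.** A reader might extend the criticism to a 2×2 reading. The documents do not support that. In such a layout the frequency main effect and the interaction both separate success from failure. Section 5.1 also leaves combined 600 Hz and 20 Hz stimulation to a future project.

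**It is a pilot.** A reader might infer that a false claim is likely, or that the next project hangs on this p-value. Neither follows. This is a case series of 8 with no power claim, and the condition for the next project is worded as evidence, not as p<0.05. The 7 to 48% figures need a rule found nowhere in the documents; the more usual follow-up gives 1.5 to 2.5%.

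**The paired contrast does not by itself prove inhibition.** This also stands. Low frequency is recorded "using the stimulation parameters (i.e., frequency, pulse width, and amplitude) that the study participant typically uses to empty their bladder", whereas 600 Hz is repeated at three recruitment levels. Suppose there is no inhibition, pressure is proportional to recruitment, and low frequency represents full recruitment. The paired contrast would then come out significantly lower in 14, 41, 73, 93% of studies at threshold, 6, 14, 25, 41% at the 50% level and 3.1, 3.7, 4.5, 5.4% at the 90% level (D = 0.5, 1, 1.5, 2). Hence the caveat in the fix.

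**Conclusion.** Wrong as written: the stated test does not test the stated hypothesis. On the natural three-condition reading, the ANOVA rejects equally often when 600 Hz works completely and when it does not work at all (14, 44, 80, 97% over the assumed range). The percentages rest on assumed effect sizes, and the exact equality on equal variances and one value per condition. The underlying mismatch does not: an overall F test cannot say which means differ or in which direction. The data remain usable, and the consequence is limited by the pilot setting and by the absence of any formal gate on the p-value. The plan should be corrected before analysis.

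**What to change.** In Section 5.6:
- Make the primary test for each aim the within-participant paired difference: sustained 600 Hz pressure, after the onset response of about 1 to 2 seconds, minus pressure at the usual low-frequency setting for that aim. Test two-sided at 0.05 with a 95% CI, and claim a reduction only if the difference is negative.
- Make the three-condition ANOVA and the comparisons with rest secondary.
- Name in advance which one of the three recruitment levels already being tested enters the contrast, and report the other two as secondary. State that at lower recruitment levels a lower 600 Hz pressure may reflect lower recruitment and not inhibition.
- In Section 5.1 (Clinical Impact), tie the evidence required for the next project to the Aim 1 contrast.

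The cost is a few sentences, with the same visits, stimulation and data. Nominal power is up to about 7 points below the overall F (41 against 44%, 73 against 80%, 93 against 97% at D = 1, 1.5, 2), but the F answers a different question.

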[1669332] High-frequency sacral root stimulation to improve bladder and bowel emptying following SCI

Funding Agency: Department of Veterans Affairs

Principal Investigator/Study Chair: [name]

Version 1.6
2 February 2023

Abstract

This is a 2-year case series study. Study participants will act as their own controls. This study will determine if sacral root stimulation at 600 Hz limits urethral sphincter contractions in individuals with SCI who have already been implanted with a Finetech-Brindley SARS system. The Finetech-Brindley SARS system is an FDA-approved device (Humanitarian Use Device) and we have received an IDE for testing this device at 600 Hz. In an initial visit lasting about 1 hour, we will complete an informed consent process to enroll the participant and collect a urine sample to test for a UTI. In a second visit lasting about 4 hours, we will conduct experiment procedures. Bladder and urethral sphincter pressures will be recorded using standard clinical urodynamics techniques. In a urodynamics laboratory, we will collect baseline data in response to the typical stimulation parameters that the participant uses for their daily bladder management. We will then test 600 Hz stimulation to determine whether this results in reduced sphincter contraction (Aim 1). The Finetech-Brindley device can also be programmed to achieve bowel emptying and return of bowel control is an extremely high priority for individuals with SCI [7]. Therefore, we will leverage the opportunity of this pilot study to determine if 600 Hz sacral root stimulation also has the potential to improve bowel emptying by reducing anal sphincter pressure (Aim 2). Participants will be asked to participate in experiments for both Aim 1 and Aim 2. Study participants who are Veterans will be consented and tested at the Cleveland VA Medical Center. Participants who are not Veterans will be consented and tested at the MetroHealth Medical Center. An IRB protocol for this study has already been approved at the MetroHealth Medical Center.

List of Abbreviations

CRC – Clinical Research Center
DSD – detrusor-sphincter dyssynergia
FES – functional electrical stimulation
LSCVAMC – Louis Stokes Cleveland Department of Veterans Affairs Medical Center
NIDDK - National Institute of Diabetes and Digestive and Kidney
NIH – National Institute of Health
SARS - sacral anterior root stimulation
SCI - spinal cord injury
SCI&D - Spinal Cord Injury & Dysfunction
TDL - Technical Development Laboratory

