If this project demonstrates evidence of urethral sphincter pressure reduction in response to 600 Hz stimulation, then we will propose in a subsequent project to apply 600 Hz stimulation to individuals with SCI in whom sacral reflexes are intact. We would implant a SARS device without the rhizotomy, and determine if reflex contractions of the sphincter can be prevented during bladder emptying. In this way, we plan to achieve efficient, catheter-free, on-demand bladder emptying using sacral root stimulation without the need for a posterior rhizotomy.

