We will then test stimulation at 600 Hz. This testing can be done simultaneously with 600 Hz testing for Aim 1. The stimulation amplitude will be set to 0 mA and gradually increased to determine the threshold amplitude for evoking an initial onset response of the anal sphincter. We will continue to increase the stimulation amplitude until we have achieved maximal anal sphincter pressure onset response. Stimulation will be maintained for up to 10 seconds with at least 30 seconds rest between stimuli. Once this recruitment curve is established, we will repeat stimulation at threshold, 50% maximal recruitment, and 90% maximal recruitment for up to 30 seconds to measure reduction of anal sphincter pressures.

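### Section 5.6 plans an ANOVA with no participant term or unit of analysis, although the 8 participants are their own controls

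*Combined protocol and SAP*

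**What the plan says.** The abstract states the design: "Study participants will act as their own controls". Section 5.1 repeats it and sets the number enrolled at 8, with stimulation testing in a single session. Section 3.0 states a two-condition hypothesis, that "sacral root stimulation at 600 Hz will result in lower urethral sphincter pressures compared to pressures in response to stimulation at the lower frequencies" usually used for the implant.

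Section 5.5 gives several 600 Hz runs per participant. Under Aim 1 a recruitment curve is built, and then "we will repeat stimulation at threshold, 50% maximal recruitment, and 90% maximal recruitment for up to 30 seconds". Aim 2 uses the same layout for the anal sphincter, "to measure reduction of anal sphincter pressures".

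The analysis plan in section 5.6 is one sentence on method: "Distributions of pressures without and with 600 Hz and 20 Hz stimulation will be compared with an ANOVA and a significance level of 0.05". It is followed by the expectation that pressures will be lower at 600 Hz. No error term, planned contrast, unit of analysis or rule for summarising runs appears there or elsewhere.

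**The concern.** The design pairs the conditions within a person, but the stated test does not say that it uses the pairing. With 8 participants, the within-person comparison is the main source of precision.

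If participant is left out and each condition contributes one value per person, the standard error contains between-person variation that the paired difference removes. With similar SDs, the main risk is missing a moderate reduction in pressure.

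The error can also run the other way. Section 5.5 contrasts a low frequency that evokes contraction with 600 Hz, at which, after a brief onset response, "the urethral pressure is expected to return to baseline". The low-frequency SD could therefore be larger. In that case an error term pooled over three conditions, or runs counted as independent observations, can make the standard error too small.

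The Clinical Impact text in section 5.1 makes the follow-on project, implantation without rhizotomy, conditional: "If this project demonstrates evidence of urethral sphincter pressure reduction in response to 600 Hz stimulation".

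**Working it through.** **Inputs.** From the documents: n = 8 (section 5.1); significance level 0.05 (section 5.6), taken as two-sided; two conditions in the hypothesis (section 3.0); three in the analysis (section 5.6: none, 600 Hz, 20 Hz). The documents give no SD, correlation, effect size or power, so there is no stated figure to reproduce.

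Assumed: within-person correlation ρ from 0 to 0.8; r = low-frequency SD / 600 Hz SD from 1 to 3; resting SD equal to the 600 Hz SD; one value per participant per condition, except in step 3.

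**Step 1: interval width, ordinary ANOVA divided by paired.** With the 600 Hz SD set to 1, the half-widths are:

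- paired: t(7) × √[(1 + r² − 2ρr)/8], t(7) = 2.365
- ordinary, two conditions: t(14) × √[(1 + r²)/8], t(14) = 2.145
- ordinary, three conditions: t(21) × √[2·MSE/8], MSE = (2 + r²)/3, t(21) = 2.080

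Example, two conditions, r = 1, ρ = 0.8: (2.145/2.365) × √(2/0.4) = 0.907 × 2.236 = 2.03.
Example, three conditions, r = 3, ρ = 0: (2.080/2.365) × √(7.333/10) = 0.879 × 0.856 = 0.75.

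| Layout | r | ρ = 0 | ρ = 0.5 | ρ = 0.8 |
|---|---|---|---|---|
| Two conditions | 1 | 0.91 | 1.28 | 2.03 |
| | 2 | 0.91 | 1.17 | 1.51 |
| | 3 | 0.91 | 1.08 | 1.26 |
| Three conditions | 1 | 0.88 | 1.24 | 1.97 |
| | 2 | 0.79 | 1.02 | 1.31 |
| | 3 | 0.75 | 0.90 | 1.04 |

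With two conditions the widths are equal at ρ of about 0.18 (r = 1) and 0.30 (r = 3). With three, they are equal at about 0.23 and 0.72.

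In simulation (100,000 trials per setting), the nominal 95% ordinary interval with three conditions covered 99.0% at r = 1, ρ = 0.5; 99.9% at r = 1, ρ = 0.8; and 89.6% at r = 3, ρ = 0. The paired interval covered 95% throughout.

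**Step 2: power, two conditions.** Effects are in units of the root-mean-square SD of the two conditions (40,000 replicates). Paired power at 0.8 SD was checked against the exact noncentral t.

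| Effect | r | Ordinary, ρ = 0.5/0.7/0.8 | Paired, ρ = 0.5/0.7/0.8 |
|---|---|---|---|
| 0.8 SD | 1 | 28/26/24% | 50/71/86% |
| 0.8 SD | 3 | 31/31/30% | 38/44/48% |
| 1.5 SD | 1 | 86–91% over this range | 95–100% |
| 1.5 SD | 3 | 83–85% over this range | 87–94% |

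**Step 3: false positives if runs are pooled.** Three 600 Hz runs per person are set against one low-frequency run and all are treated as independent. The settings are ρ = 0.3, 0.5, 0.7, 0.8, crossed with a participant-by-condition share of the remaining variance of 0, 0.3, 0.5, 0.7 (4 × 4 = 16 settings per r; 20,000 replicates each). Amplitude levels are treated as exchangeable.

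| r | Pooled runs, nominal 5% |
|---|---|
| 1 | 0.1–6.0% |
| 2 | 4.2–13.4% |
| 3 | 11.3–19.6% |

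The paired t test stays at 4.7–5.4% in all settings.

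**Step 4: the repeated-measures reading.** A three-condition repeated-measures ANOVA without a sphericity correction has a false-positive rate of 4.9–5.2% at r = 1, 6.0–7.3% at r = 2 and 7.4–8.5% at r = 3 (ρ from 0 to 0.8). With Greenhouse-Geisser the rates are 3.7–4.0%, 4.4–5.1% and 4.9–5.1%.

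**The case against.** The strongest reply is that this is an ambiguity, not a demonstrated wrong test. The term ANOVA includes the repeated-measures form, and a protocol that twice says participants are their own controls is most naturally read that way. This stands, and it makes the width and power figures conditional on the ordinary form. It does not close the gap. A repeated-measures ANOVA over three conditions is an omnibus test that does not isolate the section 3.0 hypothesis, it exceeds 5% when SDs differ (step 4), and it still lacks a unit of analysis and a chosen 600 Hz level.

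Other points also carry weight:

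- The width ranges straddle 1 and rest wholly on assumed values. The three-condition range also depends on the resting SD: if that were up to 3 times both stimulation SDs, the upper end would be about 3.8.
- The expected contrast may be large. At an assumed 2 SD and ρ of 0.5 to 0.8, ordinary versus paired power is 98.8–99.6% versus 99.8–100% at r = 1, and 97–98% versus 98–99.7% at r = 3, so little is lost.
- The pooled-run layout is a construction. Section 5.6 does not say that runs will be pooled, the three amplitude levels differ by design, and rates of 11% or more throughout need r = 3.
- This is an 8-person case series, described as a pilot in the abstract. The follow-on project needs evidence of a reduction, not p < 0.05.

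These points limit the consequence. They do not supply the missing specification.

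**Conclusion.** The concern holds as under-specification of the only planned test; it should be fixed before analysis. Confidence is medium, because the size depends on quantities that the documents do not give. Taken as an ordinary ANOVA, the plan gives a wrong standard error in most settings. It is too large with similar SDs once the correlation exceeds about 0.2. It can be too small when the low-frequency SD is much larger and three conditions share an error term, or when runs are pooled. If the true effect is very large, the practical loss of power is small.

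**What to change.** In section 5.6, for each sphincter:

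- Define one summary pressure per participant per condition, at one 600 Hz amplitude level named in advance by the investigators.
- Make the primary analysis the within-participant difference, 600 Hz minus low frequency, with a paired t test and its 95% confidence interval.
- Make any three-condition comparison a repeated-measures ANOVA with a sphericity correction such as Greenhouse-Geisser.
- If run-level data are kept, analyse them secondarily in a mixed model with random effects for participant and participant-by-condition.

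A prespecified repeated-measures contrast would also respect the design. The paired difference is the simplest form and answers the section 3.0 hypothesis directly.

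The cost is one or two sentences and no new data. Error degrees of freedom for the two-condition contrast fall from 14 to 7. If the within-person correlation were zero, power at 0.8 SD would be about 28% instead of 32%. With equal SDs, Greenhouse-Geisser is slightly conservative: power at 0.8 SD and correlation 0.5 is 49%, against 54% uncorrected.
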